Attachment 5: Thrombotic Events to be Reported as Potential AESIs

At the time of protocol amendment 5 writing, the list of thrombotic events to be reported to the sponsor as potential AESIs is provided below. Further guidance may become available on thrombotic events of interest.

- MedDRA PTs for large vessel thrombosis and embolism
 - Aortic embolus, aortic thrombosis, aseptic cavernous sinus thrombosis, brain stem embolism, brain stem thrombosis, carotid arterial embolus, carotid artery thrombosis, cavernous sinus thrombosis, cerebral artery thrombosis, cerebral venous sinus thrombosis, cerebral venous thrombosis, superior sagittal sinus thrombosis, transverse sinus thrombosis, mesenteric artery embolism, mesenteric artery thrombosis, mesenteric vein thrombosis, splenic artery thrombosis, splenic embolism, splenic thrombosis, thrombosis mesenteric vessel, visceral venous thrombosis, hepatic artery embolism, hepatic artery thrombosis, hepatic vein embolism, hepatic vein thrombosis, portal vein embolism, portal vein thrombosis, portosplenomesenteric venous thrombosis, splenic vein thrombosis, spontaneous heparin-induced thrombocytopenia syndrome, femoral artery embolism, iliac artery embolism, jugular vein embolism, jugular vein thrombosis, subclavian artery embolism, subclavian vein thrombosis, obstetrical pulmonary embolism, pulmonary artery thrombosis, pulmonary thrombosis, pulmonary venous thrombosis, renal artery thrombosis, renal embolism, renal vein embolism, renal vein thrombosis, brachiocephalic vein thrombosis, vena cava embolism, vena cava thrombosis, truncus coeliacus thrombosis
- MedDRA PTs for more common thrombotic events
 - Axillary vein thrombosis, deep vein thrombosis, pulmonary embolism, MedDRA PTs for acute myocardial infarction*, MedDRA PTs for stroke*

Source: Shimabukuro T. CDC COVID-19 Vaccine Task Force. Thrombosis with thrombocytopenia syndrome (TTS) following Janssen COVID-19 vaccine. Advisory Committee on Immunization Practices (ACIP). April 23, 2021. https://www.cdc.gov/vaccines/acip/meetings/slides-2021-04-23.html.

*Vaccine Adverse Event Reporting System (VAERS) Standard Operating Procedures for COVID-19 (as of 29 January 2021) https://www.cdc.gov/vaccinesafety/pdf/VAERS-v2-SOP.pdf

INVESTIGATOR AGREEMENT

I have read this protocol and agree that it contains all necessary details for carrying out this study. I will conduct the study as outlined herein and will complete the study within the time designated.

**ABBREVIATIONS**

ADCP	antibody dependent cellular phagocytosis
AE	adverse event
BAMA	binding antibody multiplex assay
BIDMC	Beth Israel Deaconess Medical Center
BMI	body mass index
CI	confidence interval
CRF	case report form
CTP	clinical trial protocol
DAIDS	Division of AIDS
DP	drug product
DPS	data presentation specification
ELISA	enzyme-linked immunosorbent assay
ELISPOT	Enzyme-Linked ImmunoSpot
ENV	Envelope
FHCRC	Fred Hutchinson Cancer Research Center
GM	geometric mean
GMR	geometric mean ratio
HIV	human immunodeficiency virus
ICS	intracellular cytokine staining
IG	immunogenicity
LLOQ	lower limit of quantification
LOD	limit of detection
PrEP	Pre-Exposure Prophylaxis
SAE	serious adverse event
SDTM	study data tabulation model
ULN	upper limit of normal
VRC	Vaccine Research Center
WBC	white blood cell

**DEFINITION OF TERMS**

Randomization	1:4:1 ratio			
Study vaccine	
 
- Ad26.Mos4.HIV (Ad26.Mos.1.Env + Ad26.Mos.2.Env + Ad26.Mos1.Gag-Pol + Ad26.Mos2.Gag-Pol): Total dose is <math>5 \times 10^{10}</math> viral particles (vp) per 0.5 mL injection
 
- Clade C gp140 DP: gp140 DP with 250 mcg total protein, mixed with aluminum phosphate adjuvant (0.425 mg aluminum) at the pharmacy, per 0.5 mL injection
 
- Clade C + Mosaic gp140 DP: a combination of Mosaic gp140 [125 mcg] and Clade C gp140 [125 mcg], mixed with aluminum phosphate adjuvant (0.425 mg aluminum) at the pharmacy, per 0.5 mL injection
 
- Placebo: 0.9% saline, 0.5 mL injection
 
			
Vaccination compliance	Each vaccine administered (if applicable) according to planned schedule			
Vaccine regimen	Group	Planned N	Day 1, Week 12	Week 24, Week 48
	1	25	Ad26.Mos4.HIV	Ad26.Mos4.HIV + Clade C gp140
	2	100	Ad26.Mos4.HIV	Ad26.Mos4.HIV + Clade C + Mosaic gp140
	3	25	Placebo	Placebo + Placebo

## 1. INTRODUCTION

This statistical analysis plan (SAP) is applicable to all data available up to the end of the study.

The purpose of this document is to include the analyses for the late boost and the long term extension part of the study. For completeness, the description of the analyses regarding the data up to Week 72 are kept in this document but the outputs will not be repeated when data after Week 72 become available.

All the below described analyses are supposed to be performed on fully unblinded data.

### 1.1. Trial Objectives

See CTP, Section 2.1.

### 1.2. Trial Design

See CTP, Section 3.1.

### 1.3. Statistical Hypotheses for Trial Objectives

No formal statistical hypothesis will be tested.

### 1.4. Sample Size Justification

See CTP, Section 11.2.

### 1.5. Randomization and Blinding

See CTP, Section 5.

## 2. GENERAL ANALYSIS DEFINITIONS

A baseline (or reference) value will be defined as the value of the last available assessment performed prior to the first dose (active vaccine or placebo).

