## 6. IMMUNOGENICITY

### 6.1. Analysis specifications

The analysis of immunogenicity will be done on the PPI analysis set (Section 2.3). Data and timepoints from the subjects receiving the late boost vaccination will be reported also separated from the previous time points however the same rules defined for the main part of the study will be applied.

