#### Humoral response

For all the humoral assays the immune response values will be  $\log_{10}$ -transformed before any further handling. The  $\log_{10}$ -transformed values will be used throughout the analysis. In the graphs, original values will be displayed on the  $\log_{10}$  scale.

For each assay and at each time point geometric mean of actual values, geometric mean increases and percentage of responders, all with corresponding 95% CIs will be provided by group in the tables. Within each group, the mean fold change of Week 52 to Week 72 will be reported. The definition of responders is defined in section 6.4. for each assay. Graphical presentations will be provided displaying dots for the subject values and including the geometric mean and the percentage of responders. If available, baseline values will be summarized pooling all the groups and will be displayed on the left of each graph. Data from post-baseline timepoints will be plotted next to each other for each group, a symbol will identify the geometric mean (or the median) of each group and timepoint.

In the graphs the actual values will be shown and the LLOQ cut-off will be visualized, the values below LLOQ or below LOD will be visualized with the value imputed as described in section 6.3.

Graphs by subgroups listed in section 2.4 will be done for ELISA (Clade C C97ZA.012, Mos1) and for ADCP (Clade C C97ZA.012), Mos1).

Durability will be displayed as a line plot showing the GM/median for each vaccine regimen.

Magnitude-breadth (MB) plot for the ELISA assay will be provided at post-baseline timepoints to explore the magnitude and breadth of each individual serum sample assayed (antibody titers of 5 Clades). MB curves will show, for each possible titer threshold, the proportion of antibody titers greater than this threshold. The group-specific curve obtained as the average MB across all subjects in that group will be displayed. The AUC-MB is calculated as the average of the titers over the panel of antigens.

For BAMA the median will be reported instead of the geometric mean. Cumulative number of responses across the IgG/antigen classes will be tabulated.

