### **Cellular response**

For ELISpot and for each peptide: n, median, quartile range, min, max of actual values, percentage of responders above a predefined threshold (see section 6.4) and corresponding 95% CI will be tabulated.

Graphical presentations will be provided displaying dots for the subject values and including the median and the percentage of responders. In the graphs the actual values will be shown and the LLOQ cut-off will be visualized, the values below LLOQ will be visualized with the value imputed as LLOQ/2.

In the graphs, original values will be displayed on the  $\log_{10}$  scale. Graphs by subgroups listed in section 2.4 will be done for ELISpot Env peptide pool PTE, Gag peptide pool PTE and Pol peptide pool PTE.

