**6.4. Handling of Missing and/or Invalid Immune Response Data**

Analysis will be carried out on the available data, no imputation will be done for missing samples. BAMA and ICS unreliable values should be excluded from the analysis: those records will be flagged in the SDTM dataset.

LLOQs by assay/test are listed in section 6.5. Values below LLOQ or LOD will be handled as follows:

- Calculation of Geomean (humoral response except ADCP) and median (cellular response):
  - o values < LLOQ are imputed =LLOQ/2
  - o values = LOD are imputed =LLOQ/2

For ADCP only:

- o values < LOD are imputed =LOD/2

- Calculation of fold increases from baseline:
  - o values <LLOQ are imputed =LLOQ
  - o values =LLOQ are imputed = LLOQ

For ADCP only:

- o values < LOD are imputed =LOD

Values above the upper limit of quantification (ULOQ) will be handled as follows:

- Calculation of geomean and median:
  - o Values>ULOQ are imputed=ULOQ.
- Calculation of fold increases from baseline:
  - o Values >ULOQ are imputed with ULOQ

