**6.5. Immune response assays: details**

The details for each immune response assay are listed in following table. The final framework will be reported in the DPS, as not all details might be available at the time this SAP has to be approved.

Assay	Test	Lab	LLOQ a	LOD a	ULOQ a	Unit	Responder definition/Positivity (if baseline is not available)
ELISA	Ad26 VNA	Janssen Vaccines and Prevention	17	NA	NA	IC90	>LLOQ
Env ELISA IgG-t gp140	Clade A (92UG037.1) Clade B (1990a) Clade C (Con C) Clade C (C97ZA.012) Mos1	Janssen Vaccines and Prevention	625 156.25 625 156.25 78.125	0	1600000 800000 1600000 1250000 1250000	EU/ml	1) if baseline <LLOQ or missing, R>LLOQ 2) if baseline >=LLOQ, R=3-fold increase from baseline
Env ELISA IgG1-3	Clade C (C97ZA.012) IgG1 Clade C (C97ZA.012) IgG3	BIDMC	12.3 12.4	4	403.4 120.8	EC50	
Env ADCP gp140	Clade A (92UG037.1) Clade B (1990a) Clade C (Con C) Clade C (C97ZA.012) Mos1	Ragon	NA	5.16 6.43 6.49 4.32 4.28	NA	PS	1) if baseline <LOD or missing, R>LOD 2) if baseline >=LOD, R=3-fold increase from baseline
VNA	TZM-bl Clade B (6535.3) TZM-bl Clade B (BZ167.12) TZM-bl Clade B (Bx08.16) TZM-bl Clade B (SF162.LS) TZM-bl Clade B (SS1196.1)	Seaman (BIDMC)	20	NA	43740	ID50	>LLOQ
TZM-bl b	Clade C (MW965.26) Clade C (97ZA012.12) b Clade C (ZM233M) Clade C (CE703010010) Clade C (2759058)	Duke U	10	NA	21870	ID50	>LLOQ

a In case final LLOQ and ULOQ values present in the dataset differ from those listed in this table, those provided from the lab should be used.

b At Week 52 samples that have a titer >500 against MW965.26 or >50 against 97ZA012.12 at Week 28 will be assayed against ZM233M, CE703010010, 2759058, ZM215F, SO431, CE704810053.  
Samples that have a titer >50 against MW965.26 at visit 15 (Wk52) will be assayed against MW965.26 at visit 17 (Wk72). Samples that have a titer >10 against 97ZA012.12 at visit 15 (Wk52) will be assayed against 97ZA012.12 at visit 17 (Wk 72).

Assay	Test	Lab	LLOQ a	LOD a	ULOQ a	Unit	Responder definition/Positivity (if baseline is not available)
	Clade C (ZM215F) Clade C (SO431) Clade C (CE704810053)						

BAMA IgG3	HIV ENV Con S gp140 CFI (Clade M) HIV ENV Con 6 gp120/B (Clade M) HIV ENV gp41 HIV ENV 1086C_D7gp120 (Clade C) HIV ENV 1086C gp140 (Clade C) HIV ENV 1086C_V1V2 (Clade C) HIV ENV gp70_B.Case A_V1V2 (Clade B)	Duke U	100 e	NA	NA	MFI	BAMA interpretation= 1

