BAMA Breadth	HIV ENV gp120 Clade A (51802) IgG-t Ab Clade AE (254008) IgG-t Ab Clade AE (A244) IgG-t Ab Clade B (B.6240) IgG-t Ab Clade B (BORI) IgG-t Ab Clade B (TT31P) IgG-t Ab Clade BC (CNE20) IgG-t Ab Clade BC(BJOX002) IgG-t Ab Clade C(1086C_D7) IgG-t Ab B Clade M (Con 6) IgG-t Ab +12 more (will be listed in DPS) HIV ENV gp140 Clade B (SC42261) IgG-t Ab Clade C (CH505TF) IgG-t Ab C Clade A (9004S) IgG-t Ab						

e This is not LLOQ but “positive” threshold as provided by the lab

	C Clade B (RHPA) IgG-t Ab C Clade B (WITO)IgG-t Ab C Clade C (1086C) IgG-t Ab C Clade C (BF1266) IgG-t Ab CF Clade AE (conAE) IgG-t Ab CFI Clade M(Con S) IgG-t Ab  HIV ENV gp41 IgG-t Ab  HIV ENV gp70 Clade A (191084)IgG-t Ab Clade AE (C2101) IgG-t Ab Clade AE (CM244) IgG-t Ab Clade B (62357.14) IgG-t Ab Clade B (CaseA) IgG-t Ab Clade B (RHPA4259) IgG-t Ab Clade B (TT31P) IgG-t Ab Clade B(700010058) IgG-t Ab Clade BC (BJOX) IgG-t Ab Clade C (96ZM651) IgG-t Ab Clade C (BF1266) IgG-t Ab Clade C (CAP210) IgG-t Ab Clade C(Ce1086) IgG-t Ab Clade C(TV1.21)IgG-t Ab Clade C (001428)IgG-t Ab Clade C (7060101641)IgG-t Ab							
ELISpot	Env peptide pool Mos1 Pol peptide pool Mos1 Gag peptide pool Mos1 Env peptide pool Mos2 Pol peptide pool Mos2 Gag peptide pool Mos2	BIDMC	55	0	NA	SFC/10  PBMC	1) if baseline <threshold or missing, R>threshold 2) if baseline >=threshold, R=3-fold increase from baseline	73 g 112 87 70 63 55 100

g Threshold for ELISpot test is based on the 95 percentile from the baseline values of about 350 subjects on that test in the HIV-V-A004 study

	Env peptide pool PTE f (Env peptide pool 1 PTE, Env peptide pool 2 PTE, Env peptide pool 3 PTE) Pol peptide pool PTE Gag peptide pool PTE							105 181
ICS (CD4+, CD8+)	Combined pools HIV Gag pep pool HIV Pol pep pool (Mos1) HIV ENV pep pool (Mos1 ZA) HIV Env Pol Gag pep pool  Separated pools HIV Pol RT pep pool (Mos1) HIV Gag pep pool (Mos1) HIV Pol RNaseInt pep pool 1 (Mos1) HIV ENV gp120 pep pool 1 (Mos1) HIV ENV gp41 pep pool 1 (Mos1) HIV ENV gp120 pep pool clade C (ZA) HIV ENV gp41 pep pool clade C (ZA) HIV ENV pep pool 1 (Mos2)	FHCRC	NA	NA	NA	% of CD4+/C D8+ T cells	ICS interpretation=1 for cytokine combination: IFN+ or IL2+. Otherwise Fisher exact test comparing for each antigen the total cytokine count of the considered antigen with the sum of total cytokine counts in the negative controls.	

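### Post-late-boost fold increases and ELISA, ADCP and ELISpot responder status are scored against the value before Dose 1, so they mix the persisting primary response with any boost effect

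*SAP*

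**What the plan says.** SAP section 2 defines a single reference: "A baseline (or reference) value will be defined as the value of the last available assessment performed prior to the first dose". SAP 5.2, for laboratory data, makes clear that the very first vaccination is meant. SAP 6.1 says that late-boost data will also be reported separately, but "however the same rules defined for the main part of the study will be applied".

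Two kinds of summary depend on that reference:

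- **Fold increase (humoral).** SAP 6.3 tabulates, for each humoral assay and time point, "geometric mean of actual values, geometric mean increases and percentage of responders". SAP 6.4 gives the imputation rules under "Calculation of fold increases from baseline".
- **Responder status.** SAP 6.5 uses a two-part rule. For the Env IgG-total ELISA the first part is "if baseline <LLOQ or missing, R>LLOQ", for ADCP "if baseline <LOD or missing, R>LOD" and for ELISpot "if baseline <threshold or missing, R>threshold". Otherwise a 3-fold increase from baseline is required. For ELISpot, SAP 6.3 plans "percentage of responders above a predefined threshold (see section 6.4) and corresponding 95% CI will be tabulated".

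No section sets a pre-boost reference. The only other time contrasts named in SAP 6.3 are Week 52 against Week 28 and Week 52 to Week 72, all before the boost. Protocol 9.1.10 does collect a pre-dose immunogenicity sample at the late-boost visit.

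**The concern.** The late-boost extension exists to evaluate the impact of the late boost (protocol 1.3). Entry requires enrolment in the long-term extension (protocol 4.5), and that requires assignment to Group 1 or 2 and receipt of all four vaccinations (protocol 4.4). Late-boost placebo recipients are therefore fully primed.

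A placebo recipient whose level does not change is scored a responder at post-boost visits in two cases: the pre-Dose-1 value was below the cut-off and the level is still above it, or the level is still at least 3-fold above a detectable pre-Dose-1 value. The responder column then shows who is still positive since before Dose 1. The fold-increase column shows the total rise since Dose 1. Neither isolates the boost within an arm.

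This affects reported endpoints. Protocol 2.1 lists IFN-gamma PBMC responders and phagocytosis as secondary endpoints that also apply to the late boost, and the PBMC endpoint is itself a responder endpoint. SAP 6.3 gives ELISpot no fold increase to set beside the responder rate. Late-boost ELISA is exploratory.

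**Working it through.** The plan states no late-boost fold increase or responder rate, so there is no figure to reproduce. The calculation applies the SAP rules to assumed pre-boost levels.

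**Inputs from the documents.** SD 0.4 log10 (protocol 11.3); 36 active and 12 placebo, from 3:1 of 48 (protocol 3.1); ELISA LLOQ 156.25 for Clade C (C97ZA.012), and 625 as the highest LLOQ in the table (SAP 6.5); values below LLOQ set to LLOQ for fold increases (SAP 6.4).

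**Assumptions.** Pre-boost geometric mean titre (GMT) of 150 to 10,000; a true 5-fold boost; no change on placebo; all pre-Dose-1 values below LLOQ.

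**Formulas.** Let d = log10(GMT/LLOQ).

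- Responder share = Φ(d/0.4). For the boosted arm, multiply GMT by 5.
- Geometric mean fold increase = 10^[d·Φ(d/0.4) + 0.4·φ(d/0.4)], the mean of log10 titre above LLOQ with lower values set to LLOQ.

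Example, GMT 300 and LLOQ 156.25: d = log10(1.92) = 0.283, d/0.4 = 0.708, Φ = 0.761. Fold = 10^(0.283 × 0.761 + 0.4 × 0.310) = 10^0.340 = 2.2, with no true change.

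| LLOQ | Pre-boost GMT | Placebo responders | Boosted responders | Placebo fold | Boosted fold | Ratio of folds |
|---|---|---|---|---|---|---|
| 156.25 | 150 | 48% | 96% | 1.4 | 4.9 | 3.45 |
| 156.25 | 300 | 76% | 99% | 2.2 | 9.6 | 4.40 |
| 156.25 | 1,000 | 98% | 100% | 6.4 | 32 | 4.96 |
| 156.25 | 10,000 | 100% | 100% | 64 | 320 | 5.00 |
| 625 | 300 | 21% | 83% | 1.1 | 2.6 | 2.34 |
| 625 | 1,000 | 70% | 99% | 1.9 | 8.0 | 4.20 |
| 625 | 10,000 | 99.9% | 100% | 16 | 80 | 5.00 |

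The ratio of folds falls short of 5 only through LLOQ imputation.

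**Other SDs and assays.** The documents give no SD for ADCP or ELISpot. With the level at 1, 2, 5 and 10 times any cut-off, placebo responders are 50%, 77%, 96% and 99% at SD 0.4, and 50%, 69%, 88% and 95% at SD 0.6.

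**Detectable pre-Dose-1 value.** With the level still k-fold higher, the share is Φ(log10(k/3)/s), where s = 0.566 (correlation 0 between the two values) or 0.40 (correlation 0.5). For k = 3, 5 and 10 this gives 50%, 65% to 71%, and 82% to 90%.

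**Can the responder column separate the arms?** Protocol 11.4 names Fisher's exact test for discrete parameters; SAP 6.3 does not repeat it. By exact enumeration (36 against 12, two-sided p<0.05, LLOQ 156.25), power against a true 5-fold boost is 94%, 57%, 0.2% and about 0 at the four GMTs. The higher the persisting response, the less the column can show.

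**Pre-boost reference instead.** I simulated 1,000,000 pairs per setting under the two-part rule taken against the pre-boost sample (LLOQ 156.25, GMT 150 to 10,000, pre/post correlation 0.5 to 0.875). Responders are 0.8% to 18.5% on placebo, 19% to 42% with a true 2-fold boost, 50% to 60% with 3-fold and 71% to 88% with 5-fold. A t-test on mean log10 change (SD of change 0.40 to 0.20, 46 df) has 60% to 99% power at 2-fold and at least 94% at 3-fold.

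**The case against.** The strongest reply concerns reach, not the reading of the text.

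- **Most late-boost endpoints are magnitudes.** Boost-specific ELISA is titres and breadth, the Group 1 against Group 2 endpoint is relative magnitude, and phagocytosis is a score. All are available from actual values, which SAP 6.3 reports. This stands: the ADCP score itself is untouched, and of these endpoints only the PBMC one is worded as responders.
- **The randomised placebo arm rescues the fold increase.** In expectation the between-arm ratio is the same under either reference. This stands too. What remains is that one arm's fold increase, read alone, is not a boost effect, and SAP 6.3 names no active-against-placebo contrast for the late boost.
- **A constant reference helps durability.** It keeps all visits comparable. That is a reason to keep the pre-Dose-1 display, not to leave it as the only one.
- **The size is assumed.** Near-total distortion at five times the cut-off needs SD 0.4 and an undetectable pre-Dose-1 value; the alternatives above give 88% or 65% to 71%. The sister study's maintained responses to Week 120 (protocol 1.1.2.2) make persistence plausible but give no Week 192 level.
- **The 3-fold rule is blunt.** It is, so it should not be the main reading of the boost.
- **The separate data presentation specification, not among the documents, may refine assay details.** SAP 6.5 says so, but the rule stated in the SAP is the pre-Dose-1 one.

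None of this changes what the responder column will show for a primed placebo recipient.

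**Conclusion.** The concern holds and should be fixed. As written, post-boost humoral fold increases and ELISA, ADCP and ELISpot responder rates combine the persisting primary response with any boost. The distortion is modest when the persisting level is near the cut-off (placebo responders 21% to 50%, placebo fold 1.1 to 1.4 in the cases shown) and severe well above it (98% or more, and 6-fold to 64-fold, at GMT 1,000 to 10,000 with LLOQ 156.25). These figures rest on assumed pre-boost levels, the main-study SD and, for the ELISA table, undetectable values before Dose 1.

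Actual-value geometric means and medians, magnitude-breadth curves and the between-arm ratio of fold increases are not affected. TZM-bl, Ad26 VNA, BAMA and ICS positivity do not use this baseline. The IgG1/IgG3 ELISA responder cell is blank in the text available, so the ELISA point rests on the IgG-total row. The boost effect is still recoverable; two planned displays would mislead about it.

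**What to change.** 1. For time points after the late boost, add humoral fold increase and ELISA, ADCP and ELISpot responder status relative to the last sample before the late boost (Visit 22a, pre-dose), tabulated by late-boost arm.
2. Keep the pre-Dose-1 version as a separate display labelled as continued positivity.
3. State that the boost effect is read mainly from geometric mean fold change from pre-boost and from actual values, with responder status as support.
4. As a related change, use the pre-boost Ad26 titre for the late-boost Ad26 objective. Protocol 2.1 asks for antibody at the time of vaccination, whereas the SAP 2.4 subgroup uses baseline.

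The cost is SAP wording, some reprogramming and extra tables; no new sample is needed. The statistical downside is the bluntness of the 3-fold rule against the pre-boost value. With titres well above the cut-off it scores about 50% of subjects with a true 3-fold boost and 19% to 33% with a 2-fold boost. Near the cut-off it scores up to 19% of placebo recipients by chance. Item 3 is there for that reason.

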### 2.1. Analysis Windows

The phases and periods in the study will be constructed as follows:

**Table 3: Phase and Period Definitions**

Phase	Phase number	Period	Period number	Interval	
				From	To
Screening	1			00:00 of the date of signing the informed consent form a	One minute prior to Dose 1 on Day 1
Regimen	2	Post-Dose 1	1	Date and time of Dose 1 (Day 1)	Minimum of: a) Maximum (28 days after first vaccination at 23:59, scheduled visit 4 weeks after first vaccination at 23:59) b) 23:59 at the date of last contact (for early discontinuation)
Follow-Up 1	3			1 minute after end of Post-Dose 1 period	Minimum of: a) One minute prior to date and time of the next vaccination b) 23:59 at the date of last contact (for early discontinuation)
Regimen	2	Post-Dose 2	2	Date and time of Dose 2 (Day 85)	Minimum of: a) Maximum (28 days after second vaccination at 23:59, scheduled visit

Phase	Phase number	Period	Period number	Interval	
				From	To
					4 weeks after second vaccination at 23:59) b) 23:59 at the date of last contact (for early discontinuation) c) One minute prior to post-dose 3
Follow-Up 2	4			1 minute after end of Post-Dose 2 period	Minimum of: a) One minute prior to date and time of the next vaccination b) 23:59 at the date of last contact (for early discontinuation)
Regimen	2	Post-Dose 3	3	Minimum of Date and Time of the two Dose 3 Injections (Day 169)	Minimum of: a) Maximum (28 days after third vaccination at 23.59, scheduled visit 4 weeks after third vaccination at 23:59) b) 23:59 at the date of last contact (for early discontinuation)
Follow-Up 3	5			1 minute after end of Post-Dose 3 period	Minimum of: a) One minute prior to date and time of the next vaccination b) 23:59 at the date of last contact (for early discontinuation)
Regimen	2	Post-Dose 4	4	Minimum of Date and Time of the two Dose 4 Injections (Day 337)	Minimum of: a) Maximum (28 days after fourth vaccination at 23.59, scheduled visit 4 weeks after fourth vaccination at 23:59) b) 23:59 at the date of last contact (for early discontinuation)
Follow-Up 4	6			1 minute after end of Post-Dose 4 period	- If late boost vaccination took place: One minute prior to late boost vaccination ((Day 1345 – Week 192) - If no late boost vaccination took place: Minimum of: a) Last available visit for completers b) 23:59 at the date of last contact (for early discontinuation)
Late Boost	7	Post-Dose 5	5	Minimum of Date and Time of the two Late Boost Injections (Day 1345 – Week 192)	Minimum of: - Maximum (28 days after late boost vaccination at 23.59, scheduled visit 4 weeks after late boost vaccination at 23:59) - 23:59 at the date of last contact (for early discontinuation)
Follow-Up 5	8			1 minute after end of Post-Dose 5 period	Minimum of: a) Last available visit for completers b) 23:59 at the date of last contact (for early discontinuation)

